8.6.1.2 Primary Model

The primary efficacy variable will be analyzed using linear mixed effect modelling for repeated measures (MMRM) assuming data missing at random (MAR) with treatment, week, and week by treatment as fixed effects, the continuous baseline Abdominal Symptoms domain score and VH:CD ratio as covariates, and subject as a random effect.

Baseline Abdominal Symptoms domain score is defined as the average of the daily scores for the last week of the placebo run-in period. Baseline VH:CD is the measure from endoscopic biopsies performed during the placebo run-in period.

The variance-covariance structure to be used is unstructured (UN). If model convergence is not achieved, a first-order auto-regressive structure [AR(1)] will be considered. Additional variance-covariance structure might be explored in case of non-converge issue.

An overall estimate of treatment effect as well as treatment differences for the active treatment groups (600 mg, 300 mg, 150 mg) compared to placebo will be provided along with the respective 95% confidence intervals (CIs). By-week estimates and 95% CI will be provided as well. All tests of statistical significance will be at two-sided, 0.05 level of significance.

The following model will be fitted:

$$Y_{ijk} = \mu + \alpha_j + \gamma_k + \lambda_{jk} + \beta_1 \cdot baseline \ Abdominal \ Symptoms \ score_{ij} + \beta_2 \cdot baseline \ VH; \ CD \ ratio_{ij} + \eta_i + \varepsilon_{ijk}$$

where

 Y_{ijk} is the change from baseline of Abdominal Symptoms weekly domain score for subject i ($i = 1, ..., n_j$) from treatment group j (j = 1, 2, 3, 4) at week k (k = 2, 4, ..., 24),

 μ is the overall mean change from baseline,

 α_j is the fixed effect due to treatment j,

 γ_k is the fixed effect due to week k,

 λ_{ik} is the fixed interaction effect due to treatment j and week k,

 β_1 is the parameter estimate for the baseline Abdominal Symptoms score,

 β_2 is the parameter estimate for the baseline VH:CD ratio,

 η_i is the random effect due to subject i,

 ε_{ijk} is the random error term for subject i from treatment group j at week k.

The observed baseline and post-baseline values along with the change from baseline values (absolute and percent) will also be summarized by treatment group and week (Weeks 2, 4, ..., 24). Baseline and post baseline values for the weekly scores will also be listed.

Mean (±SD) line plots by treatment group will be presented for both absolute values and changes from baseline for the observed data.

The primary analysis will be conducted on mITT analysis set and repeated on the PP analysis set.

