5.1. Inclusion Criteria

Subjects must fulfill all of the following criteria at screening and, if applicable, at randomization (Visit 3) to be eligible for participation:

1. Adult males or females 18 to 70 years of age, inclusive.
2. Subjects demonstrate willingness to participate in the study and to perform all required procedures as documented by signed informed consent.
3. Subjects must have a diagnosis of celiac disease by intestinal biopsy at least 12 months prior to screening as confirmed by medical records or written physician statement.
4. Subjects must have reported attempting to follow a GFD for at least the 12 consecutive months prior to screening and must be willing to maintain their current diet for the duration of study participation.
5. Subjects must have had at least one of the following symptoms at least once per week during the month before screening: diarrhea, loose stools, abdominal pain, abdominal cramping, bloating, or gas.
6. Subjects must have a Gastrointestinal Symptom Rating Scale, Celiac Disease portion (CeD-GSRS) score of >2 at the screening visit.
7. During the 4-week single-blind placebo run-in period, subjects must have a CeD PRO Abdominal Symptoms domain weekly average score ≥ 2.5 in at least 2 of the 4 weeks prior to the randomization visit (Visit 3) AND the CeD PRO Abdominal Symptom domain weekly average scores must not trend toward improvement from the initial weekly score (defined as continued improvement in weekly scores from week to week OR $>50\%$ improvement from the initial score).
8. Subjects must have detectable (above the lower limit of detection) serum celiac-related antibodies (at least one of anti-tTG IgA/IgG or DGP IgA/IgG). However, the titer in each assay must be below 3.0 times the diagnostic cut-off value for positivity of the assay in order to confirm that the subject is trying to adhere to their GFD.
9. Subjects must have human leukocyte antigen DQ (HLA-DQ) typing consistent with known celiac disease alleles (typically DQ2 and/or DQ8) obtained before the baseline biopsy. HLA-DQ typing information supplied as part of the subject medical record is acceptable.
10. Body weight between 35 and 120 kg, inclusive.
11. Female subjects must meet the following inclusion criteria:
 - a. Women not of childbearing potential:

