9.2. Sample Size Determination

A proposed sample size of approximately 50 evaluable subjects within each treatment group would provide approximately 80% power to detect a 0.40 difference from placebo to any given active treatment group at the two-sided, 0.05 level of significance in the primary endpoint, change through Week 24 in the Abdominal Symptoms domain score in CeD PRO. These calculations are based on the assumption of a █ within-subject standard deviation (SD), as derived in the CELIM-NRCD-001 trial using the mixed effect modeling for repeated measures (MMRM) analyses. An approximate █ difference in the overall least squares (LS) means through 16 weeks in the treatment period was observed between the active (300 mg) and placebo groups. The overall estimate through 16 weeks was observed to be █ for placebo versus █ for the 300 mg treatment group. Of note, the estimated difference at week 16 was █; however, the more conservative overall difference of █ was used in the calculation of sample size. The results and their ranking are exploratory in nature, and the selection of endpoints and dose for confirmatory studies will be based on the totality of evidence. As such, these calculations are not adjusted for multiplicity.

Approximately 220 subjects will be randomized at a ratio of 1:1:1:1 to PRV-015 100 mg, 300 mg, 600 mg, or placebo (approximately 55 subjects per group). Subjects will be stratified by normal or abnormal VH:CD (i.e., <2 or ≥2) and by the CeD PRO Abdominal Symptoms domain score of <3 or ≥3 at baseline using the average of the Abdominal Symptoms domain scores over the last week of the single-blind placebo run-in period immediately before randomization. The number of subjects with Marsh score of 0 or 1 will be capped at approximately 72. Withdrawn subjects will not be replaced.

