6 STATISTICAL HYPOTHESES

The hypothesis of this study is that one or more dose groups of PRV-015 is effective in attenuating the symptoms of celiac disease compared with placebo in adult subjects with celiac disease who are symptomatic despite being on a GFD for at least 12 months.

The primary endpoint is the change from baseline through Week 24 in the score of the Abdominal Symptoms domain of CeD PRO questionnaire, compared between the 3 PRV-015 dose groups and the placebo group.

The primary endpoint will be tested for each of the 3 dose levels of PRV-015, 100 mg, 300 mg, or 600 mg against placebo, separately as follows:

H₁₀: µPRV-015 (600mg) = µPlacebo

against the alternative

H₁₁: μPRV-015 (600mg) ≠ μPlacebo,

H₂₀: µPRV-015 (300mg) = µPlacebo

against the alternative

H₂₁: µ_{PRV-015} (300mg) ≠ µ_{Placebo}, and

H₃₀: µPRV-015 (100mg) = µPlacebo

against the alternative

H₃₁: µPRV-015 (100mg) ≠ µPlacebo

where $\mu_{PRV-015~(600mg)}$, $\mu_{PRV-015~(300mg)}$, $\mu_{PRV-015~(100mg)}$ and $\mu_{Placebo}$ denote the mean change from baseline through Week 24 of Abdominal Symptoms domain score in the high dose, medium dose, low dose and placebo arm, respectively. Each of the three hypotheses will be tested using a two-sided, 0.05 level of significance with no adjustment for multiple comparisons.

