7 ESTIMATION OF SAMPLE SIZE

A proposed sample size of approximately 50 evaluable subjects within each treatment group would provide approximately 80% power to detect a 0.40 difference from placebo and any given active treatment group at the two-sided, 0.05 level of significance in the primary endpoint, change through Week 24 in the Abdominal Symptoms domain score in CeD PRO. These calculations are based on the assumption of a within-subject standard deviation (SD), as derived in the CELIM-NRCD-001 trial using the mixed effect modelling for repeated measures (MMRM) analyses. An approximate difference in the overall least squares (LS) means through 16 weeks in the treatment period was observed between the active (300 mg) and placebo groups. The overall estimate through 16 weeks was observed to be for placebo versus for the 300 mg treatment group. Of note, the estimated difference at week 16 was however, the more conservative overall difference of was used in the calculation of sample size. The results and their ranking are exploratory in nature, and the selection of endpoints and dose for confirmatory studies will be based on the totality of evidence. As such, these calculations are not adjusted for multiplicity.

Approximately 220 subjects will be randomized at a ratio of 1:1:1:1 to PRV-015 100 mg, 300 mg, 600 mg, or placebo (approximately 55 subjects per group). Subjects will be stratified by normal or abnormal baseline VH:CD (i.e., <2 or \ge 2) and by the CeD PRO Abdominal Symptoms domain score of <3 or \ge 3 at baseline using the average of the Abdominal Symptoms domain scores over the last week of the single-blind placebo run-in period immediately before

Confidential Page

randomization. The number of subjects with Marsh score 0 or 1 will be capped at approximately 72. Withdrawn subjects will not be replaced.

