8.2.2 Definition of Derived Variables

8.2.2.1 Patient-reported Assessments Captured in eDiary

CeD PRO Domain Scores

The CeD PRO is captured daily in the eDiary after the last meal of the day before the subject goes to bed. It includes 9 items asking participants about the severity of celiac disease symptoms they may experience each day. Participants are asked to rate their symptom severity on an 11-point (0 to 10) scale; from "not experiencing the symptom" to "the worst possible symptom experience". Symptoms include abdominal cramping, abdominal pain, bloating, gas, diarrhea, loose stool, nausea, headache, and tiredness (Figure 2).

[figure not shown]
Analyses will be performed on all individual domain scores and weekly worst symptom domain scores in the GI symptom domains (Abdominal Symptoms and Diarrhea/Loose Stool domains) and Total GI score (Abdominal Symptoms Domain + Diarrhea/Loose Stool Domain + Nausea item). The Total GI score will be assessed with and without inclusion of the Nausea item.

Daily mean domain score is calculated as sum of daily item scores for all items within a domain divided by number of items in the domain.

Weekly domain scores are based on analysis visit windows (defined below) and calculated as the sum of non-missing daily mean domain scores divided by the number of non-missing scores of a given week. A weekly score is calculated if there are at least 4 non-missing daily scores available. Weekly mean total GI score is calculated as the sum of weekly mean Abdominal Symptoms domain score, Diarrhea and Loose Stools domain score, and Nausea item score divided by 3. The weekly mean total GI domain score without the Nausea item, is calculated as the sum of weekly mean Abdominal Symptoms domain score, Diarrhea and Loose Stools domain score divided by 2. If any of the weekly domains are missing, the total score will be calculated as the average over the remainder non-missing weekly domain scores.

Figure 2. Symptom Domains in the Celiac Disease Patient-Reported Outcome Questionnaire

CeD PRO Symptomatic Days

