PROACTIVE Dietary Questionnaire	Most recent assessment prior to the first administration of double-blind treatment.				

Visit Windowing (post-baseline) for Patient-Reported Assessments captured in eDiary

Analysis visit windows will be applied for following patient-reported eDiary assessments for postbaseline visits and are described below:

- CeD PRO
- BSFS
- PGIS/PGIC
- Weekly Diet Questionnaire

CeD PRO analysis visit windows (for week-based analysis).

In case of missing visit, the prior visit + 14 days will be taken.

Period	Analysis Visit	Days included in analysis window
Double-blind treatment	Week 2	Days -7 to -1 prior to actual Visit 4 date
Double-blind treatment	Week 4	Days -7 to -1 prior to actual Visit 5 date
Double-blind treatment	Week 6	Days -7 to -1 prior to actual Visit 6 date
Double-blind treatment	Week 8	Days -7 to -1 prior to actual Visit 7 date
Double-blind treatment	Week 10	Days -7 to -1 prior to actual Visit 8 date
Double-blind treatment	Week 12	Days -7 to -1 prior to actual Visit 9 date
Double-blind treatment	Week 14	Days -7 to -1 prior to actual Visit 10 date
Double-blind treatment	Week 16	Days -7 to -1 prior to actual Visit 11 date
Double-blind treatment	Week 18	Days -7 to -1 prior to actual Visit 12 date
Double-blind treatment	Week 20	Days -7 to -1 prior to actual Visit 13 date
Double-blind treatment	Week 22	Days -7 to -1 prior to actual Visit 14 date
Double-blind treatment	Week 24	Days -7 to -1 prior to actual Visit 15 date

CeD PRO analysis visit windows (for month-based analysis of symptomatic days)

Period	Month	Days included in analysis window
Run-in	Baseline	Days -28 to -1 prior to Actual Visit 3 date
Double-blind treatment	1	Actual Visit 3 date (inclusive) through day prior to actual Visit 5 date if available, or Visit 3 date + 28 days (if Visit 5 is missing)
Double-blind treatment	2	Actual Visit 5 date (inclusive) through day prior to actual Visit 7 date if available, or Visit 5 date + 28 days (if Visit 7 is missing) or Visit 7 – 28 days if Visit 5 is missing
Double-blind treatment 3		Actual Visit 7 date (inclusive) through day prior to actual Visit 9 date if available, or Visit 7 date + 28 days (if Visit 9 is missing) or Visit 9 – 28 days if Visit 7 is missing
Double-blind treatment	4	Actual Visit 9 date (inclusive) through day prior to actual Visit 11 date if available, or Visit 9 date + 28 days (if Visit 11 is missing) or Visit 11 -28 days if Visit 9 is missing

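### The primary model adjusts for the last run-in week only; adding the mean of the three earlier run-in weeks as a covariate is a cheap precision gain of uncertain size

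*SAP*

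**What the plan says.** - **Collection.** Protocol 4.1 has the CeD PRO completed daily from Visit 1 (Day -28), so up to 28 daily scores precede randomization.
- **Entry.** Protocol 5.1, criterion 7, requires a weekly Abdominal Symptoms average of at least 2.5 "in at least 2 of the 4 weeks prior to the randomization visit". It also excludes subjects whose weekly scores improve continuously, or by more than 50% from the first week.
- **Primary model.** SAP 8.6.1.2 defines the baseline symptom covariate as the "average of the daily scores for the last week of the placebo run-in period". The only other baseline covariate is VH:CD. The same last-week score defines change and one stratification factor (SAP 5).
- **Minimum data.** SAP 8.2.2.1: "A weekly score is calculated if there are at least 4 non-missing daily scores available".
- **Alternative baselines.** SAP 8.6.1.5 plans two sensitivity analyses of the primary model: seven days before first dose, and ten days before randomization. The second is there because some subjects did not complete the diary daily in the week before randomization.
- **Longer window elsewhere.** A baseline month of "Days -28 to -1 prior to Actual Visit 3 date" is used, but only for the exploratory symptomatic-days analysis (SAP 8.2.2.1).
- **Secondary models.** SAP 8.6.2.1 and 8.6.2.2 adjust the Diarrhea/Loose Stool and Total GI endpoints for baseline Abdominal Symptoms and VH:CD, not for the endpoint's own baseline.

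**The concern.** A single week can be a noisy measure of a subject's usual symptom level, and whatever it misses stays in the residual. The three earlier weeks are pre-randomization measurements of the same outcome, already collected and already used to select subjects, yet they do not enter the primary model.

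The entry rule allows the last week to differ clearly from the rest. Weekly scores of 2.6, 2.5, 1.4 and 1.5 qualify:
- two weeks reach 2.5;
- the last step is a rise, so improvement is not continuous;
- the largest fall is (2.6 - 1.4)/2.6 = 46%, and the final one is (2.6 - 1.5)/2.6 = 42%.

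The model sees a baseline of 1.5, while the run-in mean is 8.0/4 = 2.0. What is at stake is the width of the interval for each dose-placebo difference, and some chance imbalance in usual symptom level that last-week adjustment does not pick up.

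**Working it through.** **1. The plan's own figure.** SAP 7 states that "approximately 50 evaluable subjects within each treatment group would provide approximately 80% power to detect a 0.40 difference", at two-sided 0.05. The SD is redacted, so the 80% cannot be reproduced independently. Solving backwards: SD = 0.40 / [(1.960 + 0.842) x sqrt(2/50)] = 0.40 / (2.802 x 0.2) = 0.714. This matches the design only because it was solved from it.

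**2. Count of diary entries.** The last week is 7 of 28 days, so 21/28 = 75% do not enter the model. With the minimum of 4 entries it is 24/28 = 86%. The ten-day sensitivity baseline still omits 18/28 = 64%.

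**3. Effect on residual variance, stable level plus independent weekly noise.** Let B be the variance of a subject's usual level, W the weekly noise variance, and D the variance of a subject-specific shift between run-in and treatment. The mean of the 12 analysis weeks has variance V = B + D + W/12. Its covariance with any run-in week is B. The residual variance is then:
- last week only: R1 = V - B²/(B + W);
- last week plus mean of the earlier three: R2 = V - B²/(B + W/4).

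All inputs here are assumptions: B = 1.3² = 1.69, W = 1.0.
- Shift SD 0.5 (D = 0.25): V = 2.023, R1 = 2.023 - 2.856/2.69 = 0.962, R2 = 2.023 - 2.856/1.94 = 0.551. Ratio 0.57.
- Shift SD 1.2 (D = 1.44): V = 3.213, R1 = 2.152, R2 = 1.741. Ratio 0.81.

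**4. With the entry rule applied.** Selection on run-in scores narrows their range and reduces the gain. In simulation with criterion 7 imposed and mean score 3.0, the two ratios become about 0.63 and 0.85. Over a grid of weekly SD 0.5 to 1.0, lag-one correlation of the weekly deviations 0 to 0.5, and shift SD 0.5 to 1.2, the ratio runs from about 0.63 to 0.95.

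**5. Strong serial correlation.** If weekly scores follow a pure AR(1) with no stable level, the last week carries everything the earlier weeks know about the future. The ratio is then exactly 1.00. With a stable level of SD 0.9, weekly SD 1.0 and AR(1) of 0.8 to 0.95, it is about 0.95 to 1.00.

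**6. Replacing instead of adding.** If the four-week mean were the only symptom covariate, residual variance under pure AR(1) with weekly correlation 0.90 to 0.95 would rise by 4% to 6% (ratios 1.043 and 1.064).

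Constant correlation with no shift and no entry rule gives ratios as low as 0.33 to 0.49. I do not use these: they assume that a subject's level on treatment is exactly that of the run-in, and they ignore criterion 7.

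**The case against.** The strongest reply is that nothing is wrong. The last-week baseline precedes randomization, is a stratification factor and is a continuous covariate, so the comparison is valid. A seven-day baseline also matches the seven-day post-baseline windows, and the 28-day window belongs to an endpoint that is itself monthly. All of this stands, and it is why the last-week score should stay. The 28-day window shows only that the longer period can be derived.

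The earlier weeks may also be less representative. The Schedule of Activities allows the baseline biopsy within 12 days before Visit 2, roughly Days -26 to -14, which falls in those weeks. Whether it disturbs symptom scores is unknown. If it does, the gain shrinks, but no bias follows, because the model estimates the covariate's weight.

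A reader might draw three stronger conclusions that the documents do not support.

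- **That most of the baseline information is unused.** This holds as a count of diary entries. In predictive terms, the last week alone captured 63% to 100% of the variance explainable from all four weeks across the correlation structures tried without the entry rule.
- **That power would rise from 80% into the mid-80s.** The arithmetic is easy: 0.143 x sqrt(0.90) = 0.135, and 0.40/0.135 - 1.96 = 1.00, giving 84%. But the planning SD is redacted and described as within-subject, whereas a subject-level covariate acts on variation between subjects. Most of the grid in step 4 also implies a last-week-adjusted SD well above 0.714 (range about 0.69 to 1.45), so the simulated gain cannot simply be attached to the plan's 80%.
- **That the baseline is biased or contradicts the entry rule.** Criterion 7 asks for only two symptomatic weeks of four. A last-week score below 2.5 is permitted and does no harm to the comparison.

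**Conclusion.** The point holds as a missed precision gain. Daily scores exist for four weeks and all four decide entry, but the primary model uses one, and the longest alternative baseline for the primary endpoint is ten days. Under the assumed structures, adding the earlier-weeks mean lowers the residual variance of the 24-week average by between 0% and about 35%. The documents give no week-to-week correlation that would place the trial within that range, and no power figure should be quoted. The case for the change is that the downside is one degree of freedom among roughly 4 x 50 = 200 evaluable subjects, while the possible gain needs no further patients or data.

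**What to change.** Before unblinding, amend SAP 8.6.1.2 as follows.

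1. Keep the last-week Abdominal Symptoms score as the baseline for change, as stratification factor and as covariate. Do not replace it with a four-week mean.
2. Add a second continuous covariate: the mean of the available weekly Abdominal Symptoms scores for the three earlier run-in weeks (three seven-day blocks covering Days -28 to -8 before randomization, with the existing four-entry rule). If all three are missing, use the last-week score.
3. In SAP 8.6.2.1 and 8.6.2.2, first add the endpoint's own last-week baseline score, then its own earlier-weeks mean. Adding only the latter would leave out the more direct baseline.
4. Carry the new covariate into the imputation model of SAP 8.6.1.3 so that it agrees with the analysis model, and list the change in SAP 8.10.

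Pooled blinded run-in data, or the earlier trial, could supply the week-to-week correlation and so indicate the likely gain. The cost is one degree of freedom in the primary model, two in each of the secondary CeD PRO models, and the derived variables. No new data are needed, and the estimand and randomization are unchanged.

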8.6.1.3 Sensitivity Analyses for Primary Model to evaluate missing data imputation methods

The primary model is a linear mixed model assuming data missing at random (MAR). Sensitivity analyses are done to assess the robustness of the primary efficacy analysis results with respect to different methods of handling missing values, under missing not at random (MNAR) assumption.

For the analysis of the primary efficacy endpoint, missing data will be imputed at the week level using Multiple Imputation (MI) after applying the visit windowing strategy for the CeD PRO weekly scores.

The MI will be carried out following 3 steps:

Step 1. Generation of imputed datasets

The PROC MI procedure of the SAS system with MCMC statement will first be used impute intermittent missingness by treatment group in order to generate 100 sets of data with monotone missingness. Subsequently, PROC MI will be used with MNAR statement indicating the neighboring-case missing values (NCMV) method (Molenberghs and Kenward, 2007) in order to impute the monotone missing values to obtain complete data sets. The imputation model will include treatment group, continuous baseline CeD PRO Abdominal Symptoms domain score, VH:CD at baseline, and CeD PRO Abdominal Symptoms weekly domain score at previous time points as covariates.

Step 2. Model-based analysis using each imputed dataset

Each of the 100 imputed datasets will be analyzed using the primary model specified in Section 8.6.1.2.

Step 3. Pooling the results from each model-based analysis

The results from the analysis of each imputed dataset will be combined using Rubin's rule (Rubin, 1987) by implementing the PROC MIANALYZE procedure of the SAS system.

8.6.1.4 Sensitivity Analyses of Primary Model to Evaluate Effect of Intercurrent Events If evaluation of intercurrent events (Section 8.6.1.1) indicates need for analysis of the primary endpoint in the presence of intercurrent events, the primary analysis will be repeated separately in the mITT analysis set addressing each of the following adjustments, after visit windowing is applied for the CeD PRO weekly data:

Prohibited Medication: Data collected prior to first use of prohibited medication will be used as observed. Time points after first use of prohibited medication will first be set to missing. The MI procedure in Section 8.6.1.3 will then be applied.

Presence of Gluten:

For subjects who do not experience presence of gluten per Section 8.6.1.1, all observed data will be used.

For subjects who experience the first presence of gluten, data from the visits prior to the presence of gluten will be used as observed. Once the first presence of gluten is experienced, observed data is only used from later visits if they meet the definition of absence of gluten. Visits exhibiting the presence of gluten will be set to missing and follow a similar multiple imputation procedure as in 8.6.1.3, with the exception that missing data will be imputed using data at those visits from placebo subjects who did not experience a presence of gluten.

Example 1 – Subject does not meet definition of presence – all observed data used

	Visit 3	Visit 5	Visit 7	Visit 9	Visit 11	Visit 13	Visit 15
Gluten Tests	Negative/ Negative	Negative/ Negative	Negative / Negative	Negative / Negative	Negative / Negative	Negative/ Negative	Negative/ Negative
Data used	Observed	Observed	Observed	Observed	Observed	Observed	Observed

Example 2 - Subject meets definition of presence at Visit 7 - imputation using placebo at visit 7

	Visit 3	Visit 5	Visit 7	Visit 9	Visit 11	Visit 13	Visit 15
Gluten	Negative/	Negative/	Positive/	Positive/	Negative/	Negative/	Negative/
Intake Tests	Negative	Negative	Positive	Negative	Positive	Negative	Negative
Data used	Observed	Observed	Presence Impute Visit 7	Presence Impute Visit 9	Presence Impute Visit 11	Observed	Observed

